2.8. Imputation Rules for Missing Concomitant Medication Dates

If a partial date is reported, it is assumed the medication (or therapy) was taken in all phases that overlap with the partial date. If both start and end dates are missing but this concomitant

medication was taken both prior to the study entry and still ongoing at study end, it is assumed medication was taken in all phases.

The rules for estimating an incomplete concomitant medication start date are as follows:

- If the month of the concomitant medication start date is equal to the month of the start of the induction phase, then the estimated start date is the DB start date;
- If the month of the concomitant medication start date is greater than the month of the start of the induction phase and earlier than the study end date, then the estimated start date of the concomitant medication is the first day of the month;
- If the month of the concomitant medication start date is greater than the month of the study end date, then no imputation will be done;
- If the month and year of the concomitant medication start date are known and the DB start date is after the month of the concomitant medication start date, then no imputation will be done;
- If either the month or year of the concomitant medication start date is missing, no imputation is to be performed.

3. SUBJECT INFORMATION

3.1. Demographics and Baseline Characteristics

Demographic and baseline characteristics (Table 2) and psychiatric history at baseline (Table 3) will be summarized by treatment group and overall for the FAS (DB), FAS (responders) and FAS (OL) (described in Section 2.4). Continuous variables will be summarized using descriptive statistics (N, mean, standard deviation [SD], median, minimum, and maximum). Categorical variables will be summarized using a frequency distribution with the number and percentage of subjects in each category. Baseline (DB) will be used for these summaries.

Table 2: Demographic Variables and Baseline Characteristics

Continuous Variables:

- Age (years)
- Baseline weight (kg)
- Baseline height (cm)
- Baseline BMI (kg/m^2) calculated as $\text{Weight (kg)}/[\text{Height (m)}]^2$

Categorical Variables:

- Age (<45 years, \geq 45 years)
- Sex (male, female)
- Baseline BMI (underweight: $<18.5 \text{ kg}/\text{m}^2$, normal: 18.5 to $<25 \text{ kg}/\text{m}^2$, overweight: $25 \text{ kg}/\text{m}^2$ to $<30 \text{ kg}/\text{m}^2$, obese: 30 to $<40 \text{ kg}/\text{m}^2$, morbidly obese: $\geq 40 \text{ kg}/\text{m}^2$)
- Employment Status
- Hypertension status^a
- Class of antidepressant (SSRI/SNRI/mirtazapine)
- Oral antidepressant
- Educational level

^a Hypertension status =Yes if SBP \geq 140mmHg and/or DBP \geq 90mmHg at least one timepoint before DB Induction Phase. Hypertension status =No if SBP<140mmHg and DBP<90mmHg at all timepoints before DB Induction Phase.

Table 3: Psychiatric History at Baseline Variables

Continuous Variables:

- Baseline MADRS total score
- Baseline CGI-S score
- Age (years) when diagnosed with MDD

Categorical Variables:

- Baseline CGI-S score
- Baseline C-SSRS category (no event, suicidal ideation, suicidal behavior)
- Number of Previous Treatments in Current Episode
- Functional Impairment based on Baseline SDS Total Score (not impaired [0-3], mild [4-11], moderate [12-19], marked [20-26] or extreme [27-30])
- Family history of
 - Depression
 - Anxiety Disorder
 - Bipolar Disorder
 - Schizophrenia
 - Alcohol Abuse
 - Substance Abuse
- Number of episodes including current episode (1, 2-3, 3<)
- Duration of the current episode (≤ 26 , $>26-52$, $>52-104$, >104 weeks)
- Use of Adjunctive antipsychotics at IC (Y/N)
- Use of benzodiazepine excluding sleep aids at IC (Y/N)
- Had been considered to be eligible for electroconvulsive therapy (Y/N)

A by-subject listing of the demographic and baseline characteristics will be provided.

Details of the medical history abnormalities will be presented in a by-subject listing.

3.2. Disposition Information

The number of screen failures will be summarized. A summary of each analysis set (defined in Section 2.4) will also be provided.

The following disposition summaries by treatment groups and overall will be provided for each phase separately.

- The number of subjects who entered a specific phase (DB induction, DB Follow-up, PT, OL induction and OL Follow-up phases)
- The number of subjects who completed a specific phase (DB induction, DB Follow-up, PT, OL induction and OL Follow-up phases)
- The number of subjects who discontinued a specific phase (DB induction, DB Follow-up, PT, OL induction and OL Follow-up phases) and their reasons for discontinuation

The number of subjects who terminated the trial and the reasons for ending study participation will also be summarized.

3.3. Extent of Exposure

Extent of exposure in terms of total duration of exposure and number of dosing sessions of intranasal study medication will be summarized by phase and treatment group for the FAS (DB), FAS (responders) and FAS (OL) (described in Section 2.4).

The total duration of exposure for the intranasal study drug and for each type of oral antidepressant (AD) during each phase is defined as the time between the first and the last dose of each type of study medication in that specific phase (last day of study medication-first day of study medication +1).

Descriptive statistics (N, mean, SD, median, minimum and maximum) of total duration of exposure of intranasal study drug will be presented for each induction phase. The total duration of intranasal study drug exposure for each induction phase will be presented using the following categories: ≤ 7 days, 8-14 days, 15-21 days, 22-25 days, > 25 days. A frequency distribution of the total number of dosing sessions of intranasal study medication for each induction phase will be presented, separately. The total duration of exposure of oral AD will be summarized similarly to the intranasal study drug, however the following categories will be used for the five analysis phases (described in Section 2.1): ≤ 7 days, 8-14 days, 15-21 days, 22-28 days, > 28 days. Each type of oral AD will be summarized separately.

Modal dose for a subject is defined as the most frequently taken dose by a subject during that phase. Mean dose of a subject is calculated as the sum of doses during the phase divided by the total number of days exposed. The final dose is the last nonzero dose received during that phase. The calculation of mean, modal and final dose will exclude days off study drug.

Descriptive statistics (N, mean, SD, median, minimum and maximum) of modal dose, mean and final dose of intranasal study drug will be presented for OL induction phase. Doses of oral AD will be summarized using descriptive statistics of the mean dose (days on drug), mode dose (days on drug) and the final dose, by each type of oral AD for each analysis phase (DB induction, DB follow-up, PT, OL induction and OL follow-up). The lowest mode dose is selected in case of ties. In addition, percent compliance of the oral AD calculated as days actual dosed/days expected to be dosed*100, will be summarized.

A by-subject listing of study drug administration and oral AD will be provided.

3.4. Protocol Deviations

Deviations that occurred during the study will be tabulated for the All Randomized analysis set by treatment group. Major deviations will be tabulated as they are grouped prior to unblinding in the following categories: subject not withdrawn as per protocol, selection criteria not met, excluded concomitant treatment, treatment deviation, noncompliance, regulatory requirement. More categories may be included depending on the nature of the protocol deviation. A subject may be counted in more than one deviation category.

A by-subject listing showing the specific major protocol deviations will also be provided.

3.5. Prior and Concomitant Medications

Antidepressant medications taken prior to the baseline visit will be summarized by treatment group for the Safety (DB) analysis set.

The number and percent of subjects who receive concomitant therapies will be summarized by phase and treatment group using the generic term of the medication for the Safety (DB) and Safety (OL) analysis sets (described in Section 2.4).

A by-subject listing of all prior and concomitant medication will also be provided.

4. EFFICACY

Efficacy summaries for the DB induction phase and the OL induction phase will be based on FAS (DB) and FAS (OL), respectively. FAS (responders) will be applied for the summaries in posttreatment phase and for the analysis for time to relapse. Summaries for DB/OL follow up phase will be based on FU(DB)/ FU (OL).

4.1. Analysis Specifications

4.1.1. Level of Significance

The primary efficacy endpoint will be evaluated at a 1-sided significance level of 0.05 (2-sided significance level of 0.1) based on MMRM pairwise comparisons using a Dunnett adjustment. For all other analyses of the primary efficacy endpoint and for all other endpoints, no multiplicity adjustment will be done and nominal p-values will be presented.

4.1.2. Data Handling Rules

As a sensitivity analysis, the change in MADRS total score will be analyzed using an analysis of covariance (ANCOVA) model, using last observation carried forward (LOCF) data. The last post baseline observation during the double-blind induction phase will be carried forward as the “End Point” for that phase. Besides the observed cases and the end point assessment, the LOCF values will be created for intermediate postbaseline time points as well. These imputed time points will be labeled ‘DAY X LOCF’.

For the analyses of responders based on MADRS total score (Section 4.3.1), remitters based on MADRS total score (Section 4.3.2), subjects with missing values will be imputed as nonresponders/nonremitters.

4.1.3. Imputation Methods for Missing Items

Imputation of the MADRS total score is described in Section 4.2.1. For all other scales where multiple items are summed to create a total, if any item of the scale is missing at a visit, the total score for that scale at that visit will be left blank.

4.2. Primary Efficacy Endpoint

4.2.1. Definition

The primary efficacy endpoint is the change in MADRS total score as measured by the change from baseline (prior to randomization) to the end of the 4-week double-blind induction phase. The MADRS is a clinician-rated scale designed to measure depression severity and to detect changes due to antidepressant treatment.⁶ The scale consists of 10 items, each of which is scored from 0 (item is not present or is normal) to 6 (severe or continuous presence of the symptoms), for a total possible score of 60. Higher scores represent a more severe condition. The MADRS evaluates apparent sadness, reported sadness, inner tension, sleep, appetite, concentration, lassitude, interest level, pessimistic thoughts, and suicidal thoughts. The test exhibits high inter-rater reliability.

If 2 or more items are missing, no imputation will be performed and the total score will be left missing. Otherwise, the total score will be calculated as sum of the nonmissing items multiplied by the ratio of the maximum number of items (ie, 10) to the number of nonmissing items.

4.2.2. Primary Estimand

The primary estimand, the main clinical quantity of interest to be estimated in the study, is defined by the following 4 components:

Population: Japanese subjects with treatment-resistant depression

Variable: change from baseline to Day 28 in the MADRS total score (see Section 4.2.1)

Intervention effect: the effect of the initially randomized treatment that would have been observed had all subjects remained on their treatment throughout the double-blind induction phase.

Summary measure: difference in variable means.

The primary analysis will be based on the FAS (DB), as described in Section 2.4.2, and the MADRS total scores collected during the double-blind induction phase.

4.2.3. Analysis Methods

Descriptive statistics of actual values and changes from baseline by treatment group will be presented for MADRS total score. The analysis of primary endpoint will only be applied for FAS (DB) during DB induction phase.

Means (+/-standard error [SE]), mean changes (+/-SE) from baseline, and least square mean changes (+/-SE) from baseline will be presented graphically in the double-blind induction phase.

4.2.3.1. MMRM

The primary efficacy variable, change from baseline in MADRS total score at Day 28 in the double-blind induction phase, will be analyzed using a Mixed-Effect Model for Repeated

Measures (MMRM) based on observed case data. The models will include baseline MADRS total score as a covariate, and treatment, day (see [Table 1](#)), and day-by-treatment interaction as fixed effects. The between-within approximation will be used to estimate the denominator degrees of freedom. The within-subject covariance between visits will be estimated via an unstructured variance-covariance matrix. In case of convergence problems, alternative variance-covariance structures will be tried in the following order, with the first structure that converges being used in the analysis: heterogeneous Toeplitz, standard Toeplitz, and AR(1) with separate subject random effect. Comparison of each esketamine dose group with the placebo group will be performed with the appropriate contrast using a Dunnett adjustment.

[figure not shown]
The change from baseline in MADRS total score over time in the double-blind induction phase will be analyzed using the same MMRM as described above.

4.2.3.2. Model Diagnostics

The normality and equal variance assumptions underlying the primary MMRM models will be assessed graphically for the MADRS total score at end point. Residuals from the primary models will be plotted against the predicted values and a QQ plot of the residuals versus the expected quantiles of the standard normal distribution will be presented. If either the equal variance or the normality assumption appears to be grossly violated, other methods including an ANCOVA on ranks model or an appropriate transformation of the primary endpoint might be considered.

4.2.3.3. MCP-Mod Analysis

Based on the MMRM, the least-squares (LS) mean estimates for each esketamine dose group and placebo group at Day 28 and the corresponding variances will be obtained. The generalized MCP-Mod approach will be applied towards the estimates obtained from the MMRM to analyze the dose-response relationship. This approach requires prespecification of a candidate model set. Using notation as in Bornkamp et al (2009)¹ the candidate set is constituted by the following 5 model profiles (with the corresponding parameters): E_{\max} ($ED_{50} = 9.33$), sigmoid E_{\max} ($ED_{50} = 44.86$, $h = 3.5$), linear, exponential ($\delta = 58.2$) and quadratic ($\delta = -0.00893$). The quadratic covers the scenario of a nonmonotonic relationship. The dose-response curves are shown below in [Figure 2](#).

Figure 2: MCP-Mod Dose Response Curves

The significance of the dose-response signal associated with each candidate model will be determined using trend tests with model-specific optimal contrast coefficients. The maximum of the candidate model trend test statistics will be used to evaluate the presence of a dose-response signal, properly accounting for multiplicity at an overall level of 5% (1-sided) using MCP-Mod methodology. If the maximum test statistic is not significant, no dose-response relationship will be further explored. Otherwise, the model families corresponding to individual candidate models with significant trend test statistic will be used to fit to the observed data and the one with the smallest Akaike Information Criterion (AIC) will be selected to represent the dose-response relationship. The corresponding confidence interval (CI) for the response at each dose will be computed based on a bootstrap approach.

4.2.3.4. Missing Data Sensitivity Analysis

The following table (Table 4) shows the assumptions of each considered analysis for the primary efficacy endpoint, all applied to FAS (DB) defined in Section 2.4.2.

Table 4: Analysis Types and Assumptions

| Analysis Type | Analysis Method | Assumption |
|----------------------|--|--|
| Primary Analysis | MMRM | Missing at Random – MAR |
| Sensitivity Analysis | ANCOVA model using change from baseline to Day 28 based on LOCF | Efficacy scores at time of discontinuation (DC) from the DB induction phase remain constant up to Day 28. |
| Sensitivity Analysis | MMRM model using change from baseline to Day 28 based on follow-up data | Efficacy scores during the DB follow-up phase can be used for the subjects who withdraw from the DB induction phase. |
| Sensitivity Analysis | Delta worsening adjustment applied to standard multiple imputation regression ^{7,8} | Efficacy scores worsen after study discontinuation |

ANCOVA

The sensitivity analysis will be based on an analysis of covariance (ANCOVA) model using change from baseline to Day 28 based on LOCF data. The models will include factors for treatment and baseline MADRS total score as a continuous covariate. A 90% CI for the difference in LSMeans and P-value will be calculated based on the contrast test statistic for each esketamine dose level.

Additional to the ANCOVA model based on LOCF method, another sensitivity analysis using the same MMRM model will be done which includes the follow-up data from subjects who discontinued the double-blind induction phase. For subjects who discontinued from the double-blind induction phase, the measures on the follow-up visit will be treated as the data ‘during DB induction phase’ and the measure within the visit window for Day 28 and closed to the target date will be used.

The delta worsening adjustment analysis will be done only if the dropout rate is larger than 15%.

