11.2. Sample Size Determination

The sample size for this study was calculated assuming a treatment difference for the double-blind induction phase of 4, 4.5, 5 points in MADRS total score between each dose (28 mg, 56 mg, 84 mg) of esketamine and the placebo respectively, a SD of 10 for each treatment group, a 1-sided significance level of 0.05 and a drop-out rate of 12.5%. A total of 183 subjects will need to be randomized to treatment in a 2:1:1:1 ratio (72 subjects on placebo group and 37 subjects per intranasal esketamine dose group) to achieve 80% power to detect difference for at least one dose group of intranasal esketamine to placebo using a Dunnett adjustment. The treatment difference and SD used in this calculation were assumed based on results of Panel B of the ESKETINTRD2003 study with clinical consideration.¹⁶

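### For the primary MADRS endpoint, the one sensitivity analysis that assumes dropouts worsen is run only above an undefined 15% dropout rate, which lies above the planned 12.5%

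*SAP*

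**What the plan says.** SAP 4.2.3.4, Table 4, sets out the primary analysis and three sensitivity analyses for change in MADRS total score at Day 28, all on the FAS (DB):

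- Primary: MMRM, valid under missing at random.
- ANCOVA on LOCF data, assuming "Efficacy scores at time of discontinuation (DC) from the DB induction phase remain constant up to Day 28".
- The same MMRM with follow-up-phase scores added for subjects who left the double-blind phase.
- Multiple imputation with a delta adjustment, assuming "Efficacy scores worsen after study discontinuation".

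The first two sensitivity analyses are unconditional. The third is not: "The delta worsening adjustment analysis will be done only if the dropout rate is larger than 15" percent. The SAP gives no arm, no denominator and no delta values.

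The planned rate is lower than the trigger. Protocol 11.2, repeated in SAP 1.4, uses "a 1-sided significance level of 0.05 and a drop-out rate of 12.5" percent, with 72 subjects on placebo and 37 on each of three doses. SAP 4.2.2 defines the primary estimand as hypothetical: the effect had every subject stayed on randomized treatment throughout the double-blind phase.

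**The concern.** The primary MMRM assumes that subjects who leave would have continued like similar subjects who stay. Of the planned primary-endpoint analyses, only the delta adjustment varies that assumption in the unfavourable direction. Placing its trigger above the expected dropout rate means that, if the trial runs as planned, it will usually not be done.

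Uneven dropout is foreseeable. Protocol 3.2.4 starts the 84 mg arm at 56 mg precisely to limit discontinuation for intolerance in that group, and Protocol 1.2 notes that Japanese subjects with TRD have had no prior treatment at 84 mg. A single pooled rate can hide loss concentrated in one arm, while the comparison at stake is that arm against placebo. Because the rate is undefined, whether the analysis is run could also be settled after dropout is known.

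**Working it through.** **Inputs.** N = 183 = 72 + 3 × 37, SD 10, effects of 4, 4.5 and 5 points, 1-sided 0.05 with Dunnett, dropout 12.5% (Protocol 11.2); trigger above 15% (SAP 4.2.3.4). The documents give no dropout rates by arm, so every arm-level rate below is an assumption.

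**Plan's own figure.** 160 evaluable / (1 − 0.125) = 182.9, which rounds up to 183. With 63 placebo and 32 per dose evaluable (72 × 0.875 = 63; 37 × 0.875 = 32.4), simulated Dunnett power for at least one dose is 78.7%, close to the stated 80%. The design reproduces.

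**Trigger read as the overall rate.** 0.15 × 183 = 27.45. So 27 dropouts (14.8%) do not trigger and 28 (15.3%) do. The chance that the analysis runs is P(X ≥ 28), X ~ Binomial(183, p):

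| True dropout | Chance the delta analysis runs |
|---|---|
| 10% | 1.6% |
| 12.5% (planned) | 15.1% |
| 15% | 48.6% |
| 20% | 95.7% |

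At the planned rate it is skipped with probability 1 − 0.151 = 0.849.

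**Heavy loss in one dose arm, overall reading.** Assumed example: 12/37 (32%) in one arm and 15/146 (10%) elsewhere gives 27/183 = 14.8%, no trigger. Summing Binomial(37, arm rate) and Binomial(146, rate elsewhere), with one arm truly at 30%:

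| Rate in the other arms | Chance of triggering |
|---|---|
| 8.1% (overall still 12.5%) | 14% |
| 10% | 34% |
| 12.5% | 64% |

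The gap is therefore real but not universal. With 18/146 (12.3%) elsewhere, the tenth dropout in the arm (10/37 = 27%) brings the total to 28 and triggers.

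**Trigger read per arm.** A dose arm exceeds 15% at 6/37 (16.2%) and placebo at 11/72 (15.3%). With every arm truly at 12.5%, the chances are 0.314 and 0.286. At least one arm exceeds with probability 1 − (1 − 0.314)³ × (1 − 0.286) = 0.77.

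The same sentence thus means about a 15% or about a 77% chance of running the analysis at the planned dropout rate.

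**What the unconditional analyses cover.** LOCF fixes the score at its last value, so it tests no further change. The follow-up MMRM uses real scores, but these are taken off intranasal drug, with further standard care arranged by the investigator (Protocol 9.1.8), so they do not target the hypothetical estimand. Subjects who withdraw consent supply none (Protocol 10.2). Neither analysis varies the size of the departure from missing at random, so neither yields a tipping point.

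**The case against.** The plan is not bare. Two sensitivity analyses are always run, and the follow-up MMRM meets the commitment in Protocol 11.4 to use data from subjects who discontinued. It can show actual worsening instead of assuming an amount, and the oral antidepressant normally continues in follow-up, which limits contamination by other treatment. This is also a Phase 2 dose-finding study, where reserving an extra analysis for material missingness is a defensible economy. All of that stands. It bears on how serious the point is, and it does not supply the missing tipping point.

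A reader might infer more than the documents support:

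- *That missing at random goes entirely untested.* It does not, given the two unconditional analyses.
- *That no analysis in the trial penalizes dropout.* SAP 4.1.2 counts missing responder and remitter values as failures, and SAP 4.3.4.1 scores early discontinuers as having no maintained response. The point is confined to the primary endpoint.
- *That LOCF tends to freeze a good early on-drug score.* Subjects who leave for reasons other than consent withdrawal have an early withdrawal visit within a week, with MADRS scheduled (Time and Events Schedule 1). Under SAP 2.1.2 that score may fall inside the double-blind phase, so the carried-forward value may already reflect some loss of effect.
- *That heavy dropout in one arm will always escape.* It can, on the overall reading and with low dropout elsewhere.
- *That a delta of a given size would overturn a 5-point result when a third of the arm is lost.* With 66 and 25 evaluable, SE = 10 × √(1/66 + 1/25) = 2.35. At a Dunnett critical value of 2.11 the margin is only 5 − 2.11 × 2.35 = 0.04. Such a result sits on the significance boundary before any delta is applied, so the example says little about the 15% condition.

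**Conclusion.** The point holds for the primary MADRS endpoint. The only analysis that assumes worsening depends on a rate that is undefined and set above the planned one. On the overall reading, which is the natural one but is not stated, it is skipped about 85% of the time at 12.5% dropout, and roughly a third of one dose arm can be lost without triggering it if the other arms stay near 10%. On the per-arm reading it would run about 77% of the time at the same true rate. These probabilities assume independent dropout at the stated rates with all 183 randomized subjects as the denominator.

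This does not show that the primary result would be biased or overturned. It is a gap in a prespecified robustness check, cheap to close. Label: cheap improvement.

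**What to change.** In SAP 4.2.3.4, delete the 15% condition. State that the delta-adjusted multiple imputation is always run for each dose versus placebo, with delta added to imputed scores in the esketamine arms over a prespecified range, and that the tipping point is reported alongside dropout by arm. The range is for the sponsor to choose and justify before unblinding. If a condition is kept, the SAP should at least define the rate (overall or per arm, with its denominator) and the delta values.

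The method is already in Table 4, so the cost is a revised sentence, programming time and one table. Nothing changes in the primary analysis, sample size or conduct.
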